# **5.0 STUDY PROCEDURES**

# **5.1 SCREENING/BASELINE PROCEDURES**

All patients who present to the University of Kansas Health System Urology clinic will be screened for participation in this study. Patients who present to the Kansas Health System Emergency Department needing urological consultation will also be screened for participation.

This an open-label, randomized, prospective study investigating the efficacy of hyoscyamine compared to tamsulosin for symptoms of stent irritation in patients undergoing routine urological procedures and requiring ureteral stent placement post-procedure. The patient would be assured that neither acceptance nor refusal would change their standard of care. The study medications are used routinely in our daily practice, and the patient would still be prescribed these medications if indicated regardless of participation in the study. Since prescribing these medicines is in our current standard of care, patients will not be withdrawn from standard of care by either participating or not participating in this study. Patients will be identified through standard of care procedures in the evaluation for the need for a ureteral stent. Routine labs (e.g. complete blood count, basic or complete metabolic panel, b-hCG, urinalysis and urine culture) and imaging will be obtained as per standard care at the provider's discretion based on the patient's history and physical exam. If a patient meets the study criteria, an informed consent will be obtained and the first Ureteric Stent Symptoms Questionnaire will be administered to establish baseline symptoms prior to the insertion of a ureteral stent.

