# **5.3 STUDY PROCEDURES**

To assess ureteral stent symptoms, we will be conducting the Ureteric Stent Symptoms Questionnaire (USSQ). The USSQ was created by Joshi et al as an instrument to measure stentrelated morbidity. The USSQ has been validated as a reliable instrument to measure the impact of ureteral stents. This validated questionnaire has been used in many previous studies regarding stent pain. In our study, the USSQ will be conducted prior to stent placement, on POD1, POD7 (or just prior to the time of stent removal if the removal occurs prior to day 7), and POD30. Basic demographic information, stent duration, stent size, stone location/size and obstructing vs. non-obstructing (if applicable), post stent insertion complications, drug diary information and questionnaire responses will be entered into a REDCap database for storage and analysis. The stent diameter will be 6Fr for all patients in the study. The appropriate stent length will be assigned to the patient based on cross sectional imaging. If cross sectional imaging is not available then stent length with be measured using a open-ended catheter to measure ureteral length. A small portion of these patients will be seen in the emergency department or while they are having an acute pain episode, so we expect that some of the pre-stenting questionnaires may not provide an accurate baseline for symptoms in these patients, hence the POD30 questionnaire will be obtained.

After informed consent is obtained, the patient will be prospectively randomized to either treatment arm in an open-label fashion using REDCap's randomization function to determine which therapy they will receive after stent placement. In the event that a patient does not find relief with their particular treatment arm, they will be permitted to receive additional narcotics or Pyridium. Should the patient continue to have unrelieved symptoms, treatment crossover is allowed since the study is designed in an intent-to-treat fashion.

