Questionnaires will be completed either in person if patient is in clinic or inpatient, or via a REDCap survey prior to stent placement, POD1, POD7 or at the time of stent removal if the removal occurs prior to day 7, and POD30. Patients with strings attach to stents will be included as there is no literature to suggest that strings cause additional stent irritation. Both medications will be stopped once the ureteral stent is removed as part of routine urological follow-up care for the primary etiology. Once the number of study participants reaches the pre-determined goal as calculated by our biostatistician, study enrollment will conclude and we will begin analyzing the data.

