# **5.5 DATA ANALYSIS**

The main hypothesis of the non-inferiority of hyoscyamine to tamsulosin for treating lower urinary tract symptoms will be tested using a t-test for non-inferiority of the change in USI between POD1 and POD7 (or day of stent removal if removed before day 7) in each treatment arm. This should be slightly more powerful than the t-test at POD7 alone that we used to estimate the sample size, but there are not enough data available for the distribution at POD1 in order to make a good estimate of the change. The non-inferiority margin will be 15% of the change in USI. The primary analysis will be conducted as intention-to-treat (ITT). That is, subjects will be analyzed as belonging to the arm they were randomized to, irrespective of later crossover or other modifications. This approach is in line with the current statement on Consolidated Standards of Reporting Trials (CONSORT). Descriptive statistics will be used to describe the results from all USSQ domains at each timepoint (i.e. mean and standard deviation, along with confidence intervals for urinary symptom index, pain symptom index, etc.). We will also conduct non-inferiority tests of change in score for ITT with hyoscyamine versus tamsulosin for the other domains spanned by the USSQ, including pain symptom index, general health index, work performance index, and sexual matters between POD1 and POD7, although we may not be wellpowered to detect non-inferiority for these additional domains.

The secondary goal of determining if there are differences in the amount of additional medications need to treat stent-related discomfort between treatment arms will be examined primarily through descriptive statistics. The drug diaries of all subjects will be used to tabulate the kinds and amounts of additional medications used. For each subject, the number of days that additional medications were used will be counted. The proportion of days that additional medications were used will be calculated for each group and 95% confidence intervals will be calculated.

Finally, we will also calculate the informed consent rate, and the discontinuation rate for those patients needing to be removed from the study in each arm.

In all cases, a p-value  $\leq$  .05 will be taken as a statistically significant result.

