# **5.6 SCHEDULE OF EVENTS**

Visits	Enrollment	Stent Placement	POD1	POD2	POD3	POD4	POD5	POD6	POD7 A	POD30
USSQ	Х		Х						Х	Х
Randomization	Х									
Complete Medication Diary		Х	Х	Х	Х	Х	Х	Х	Х	
REDCap Survey			Х						Х	Х
Stop Medication									Х	

Footnotes: A = If stent is removed prior to day seven then USSQ will occur on day of stent removal and diary will be stopped. If stent is removed after day seven then USSQ will occur on day seven but the diary will be stopped on day of stent removal.

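### The pre-stent USSQ, the only score the study drugs cannot have affected, is used only descriptively and is not required to precede the open-label allocation

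*Combined protocol and SAP*

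**What the plan says.** **Timing of the baseline.** Section 5.1 places consent first and then says that "the first Ureteric Stent Symptoms Questionnaire will be administered to establish baseline symptoms prior to the insertion of a ureteral stent". The limit it sets is stent insertion, not randomisation.

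**Timing of randomisation.** Section 5.3: "After informed consent is obtained, the patient will be prospectively randomized to either treatment arm in an open-label fashion". The assigned drug is taken once the stent is in place. The schedule in Section 5.6 marks both the USSQ and randomisation in the Enrollment column and gives no order. Its footnote concerns stent removal only.

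**Quality of the baseline.** Section 5.3 notes that a small share of patients will be seen in the emergency department or in acute pain, and says "we expect that some of the pre-stenting questionnaires may not provide an accurate baseline for symptoms in these patients". It gives this as the reason for the POD30 questionnaire. The data items listed there include obstructing status, but no marker for acute pain or emergency-department presentation.

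**Use in the analysis.** Section 5.5 tests the primary hypothesis with "a t-test for non-inferiority of the change in USI between POD1 and POD7", or to the removal day if that comes earlier. The other USSQ domains are compared on the same interval. No covariate is named. All USSQ domains at every time point, which includes the pre-stent one, are summarised with means, standard deviations and confidence intervals.

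**The concern.** POD1 is not a pre-treatment score. The drug is given after stent placement, the diary in Section 5.6 opens on the day of placement, and Section 2.2 credits hyoscyamine with an onset of 2-3 minutes. POD30 follows treatment as well. That leaves the pre-stent USSQ as the only score the drugs cannot have affected, and it enters no between-arm comparison.

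Two things are at stake. First, a collected baseline that predicts the outcome could narrow the confidence interval that is compared with the margin, and could remove the part of the arm difference that comes from chance imbalance. Second, the score is self-reported and allocation is open. If it is completed after the patient knows the drug, expectation could shift it differently in the two arms. It would then be a poor guide to baseline balance and an unsafe covariate. The second matter becomes important once the first is acted on, so the two belong together.

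**Working it through.** **Inputs from the documents.** Section 5.4: margin 15% of USI, coefficient of variation about 0.25, one-sided alpha 0.025, power 80%, about 47 per arm. Section 5.5: the sample size was based on USI at POD7 alone, while the primary test uses the change from POD1 to POD7. No correlation between the pre-stent score and any later score is given, so every correlation below is an assumption.

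**Step 1. The plan's own figure.** With a true difference of 0 and everything in units of the mean, the normal approximation is

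n = 2 × [0.25 × (1.960 + 0.842) / 0.15]² = 43.6, so 44 per arm.

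The noncentral-t version gives 45 per arm, and power at 47 per arm is 0.821. This is within two patients of the stated 47. On the log scale the answer depends on how the margin is written: 50 per arm for a ratio of 1.15 and 38 for 0.85. The stated figure is not in dispute here.

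**Step 2. Possible gain for USI at POD7.** Adjusting for a baseline with correlation r to the outcome multiplies the residual variance by 1 − r². The equivalent unadjusted size is 47/(1 − r²). The power column uses the Step 1 t calculation with SD 0.25 × √(1 − r²).

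| Assumed r | Variance removed | 47/(1 − r²) | n per arm for 80% power | Power at 47 per arm |
|---|---|---|---|---|
| 0 | 0% | 47.0 | 45 | 0.821 |
| 0.2 | 4% | 49.0 | 43 | 0.836 |
| 0.3 | 9% | 51.6 | 41 | 0.855 |
| 0.5 | 25% | 62.7 | 34 | 0.914 |

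**Step 3. Chance imbalance, also for POD7.** The standard error of the arm difference in mean pre-stent score is √(2/47) = 0.206 SD. An imbalance of one standard error moves the POD7 difference by r × 0.206 × 0.25 of the mean. That is 1.0%, 1.5% and 2.6% of the mean for r = 0.2, 0.3 and 0.5, against a margin of 15%.

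**Step 4. The planned outcome is a change.** Let a and b be the correlations of the pre-stent score with POD1 and POD7, and c the correlation of POD1 with POD7. Take equal SDs σ at both days. The covariance of the pre-stent score with the change is proportional to b − a, and the SD of the change is σ√(2(1 − c)). So the correlation with the change is

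(b − a) / √(2(1 − c)),

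and the variance removed is (b − a)² / (2(1 − c)).

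| Difference between b and a | c = 0.3 | c = 0.5 | c = 0.7 |
|---|---|---|---|
| 0 | 0% | 0% | 0% |
| 0.1 | 0.7% | 1.0% | 1.7% |
| 0.2 | 2.9% | 4.0% | 6.7% |

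If the pre-stent score predicts POD1 and POD7 equally well, differencing removes its contribution, however strong each correlation is. The same cancellation applies to Step 3. The figures in Steps 2 and 3 therefore cannot be carried over to the primary test.

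**Step 5. Order of events.** Consent, open randomisation, and then the USSQ on the same Enrollment visit satisfies Sections 5.1, 5.3 and 5.6 as written. So does consent, USSQ, and then randomisation. Nothing makes the questionnaire a condition for running the allocation.

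**The case against.** The case for leaving the plan alone is substantial.

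- **Validity.** A reader might infer that a baseline reported after open allocation biases the trial's result. It does not. Every between-arm USSQ test in Section 5.5 uses POD1 and POD7 (or removal day) only, so questionnaire order cannot reach any of them. An unadjusted t-test is valid under randomisation. This stands.
- **Deferral.** Section 5.3 allows questionnaires "via a REDCap survey prior to stent placement", and a reader might take this to mean that the baseline can be completed well after enrolment. Section 5.6 points the other way: the first USSQ is marked at Enrollment, and the REDCap survey row is blank there. Section 5.1 also describes consent and the first USSQ together, before randomisation is introduced in Section 5.3. Baseline first may well be the intent. What stands is the narrower gap that the order within the Enrollment visit is not stated.
- **Waste.** A reader might call the baseline wasted. Section 5.5 does summarise it, with confidence intervals, so it is under-used rather than wasted.
- **Unreliability.** The protocol says only that some questionnaires, in a small share of patients, may be inaccurate. The USSQ has a pain index, and obstructing status is recorded, so these patients are not wholly invisible. The documents do not support calling the baseline unreliable in general.
- **Size of the benefit.** A score taken before the stent exists may predict stent symptoms weakly, and Step 4 shows that the gain for the change score may be nil. This stands, and it limits the point to a cheap improvement.

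**Conclusion.** The point holds in a limited form. The pre-stent USSQ is the only score free of drug effect, it plays no part in any planned comparison, and its completion before allocation is not secured. The primary t-test remains valid as written. The loss is one of efficiency and of adjustment for chance imbalance.

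Its size cannot be fixed from the documents. For POD7 USI it would be 4% to 25% of the variance over assumed correlations of 0.2 to 0.5. For the planned change, under equal SDs and the values assumed in Step 4, it runs from nothing to about 7%. A reader might take the equivalents of 49, 52 or 63 patients per arm as the price paid by the primary analysis. The documents do not support that, because those figures belong to an outcome the primary test does not use.

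The change is still worth making because it is almost free, and because the order of baseline and allocation cannot be repaired after enrolment.

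**What to change.** 1. In Sections 5.1, 5.3 and 5.6, state that the pre-stent USSQ is completed and saved in REDCap before the randomisation function is run.
2. In Section 5.5, estimate the primary non-inferiority contrast from a linear model for the POD1-to-POD7 change with arm and pre-stent USI as main effects. Include no interaction with arm, so that a single arm effect is compared with the margin. The contrast stays on the scale of a difference in mean change.
3. Optionally, record acute-pain or emergency-department status at the baseline questionnaire and use it in a sensitivity analysis. With few such patients expected, it should not complicate the primary model.
4. Keep POD30 descriptive. It is a post-treatment score and should not be substituted for baseline.

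The cost is a few sentences of protocol text, a short delay before randomisation and a slightly more complex model. With 94 patients the error degrees of freedom fall from 92 to 91, so little is lost if the covariate proves uninformative. No extra visit is needed. The optional item adds one REDCap field.

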# **5.2 STUDY IDENTIFICATION**

Patient study identification (SID) will be created by the study team at the time the patient is consented and is enrolled in the study. SID will be the HSC# follow by number in chronological order. For example: HSC#-XXX.

# **5.3 STUDY PROCEDURES**

To assess ureteral stent symptoms, we will be conducting the Ureteric Stent Symptoms Questionnaire (USSQ). The USSQ was created by Joshi et al as an instrument to measure stentrelated morbidity. The USSQ has been validated as a reliable instrument to measure the impact of ureteral stents. This validated questionnaire has been used in many previous studies regarding stent pain. In our study, the USSQ will be conducted prior to stent placement, on POD1, POD7 (or just prior to the time of stent removal if the removal occurs prior to day 7), and POD30. Basic demographic information, stent duration, stent size, stone location/size and obstructing vs. non-obstructing (if applicable), post stent insertion complications, drug diary information and questionnaire responses will be entered into a REDCap database for storage and analysis. The stent diameter will be 6Fr for all patients in the study. The appropriate stent length will be assigned to the patient based on cross sectional imaging. If cross sectional imaging is not available then stent length with be measured using a open-ended catheter to measure ureteral length. A small portion of these patients will be seen in the emergency department or while they are having an acute pain episode, so we expect that some of the pre-stenting questionnaires may not provide an accurate baseline for symptoms in these patients, hence the POD30 questionnaire will be obtained.

After informed consent is obtained, the patient will be prospectively randomized to either treatment arm in an open-label fashion using REDCap's randomization function to determine which therapy they will receive after stent placement. In the event that a patient does not find relief with their particular treatment arm, they will be permitted to receive additional narcotics or Pyridium. Should the patient continue to have unrelieved symptoms, treatment crossover is allowed since the study is designed in an intent-to-treat fashion.

The first arm is hyoscyamine 0.125 mg tab sublingual every 4 hours as needed for discomfort, and the second arm is tamsulosin 0.4mg tab orally daily. Both dosing regimens are standard prescription orders. Both medications are routinely used in our practice, so patients are not being exposed to new safety risks compared to non-study patients. Risks are reasonable, as the medications used in this study are already commonly used in our daily practice. Patients will be given contact numbers for the Urology Department should they have any adverse side effects or concerns. Hyoscyamine is an anticholinergic and can cause side effects including constipation, dry mouth, drowsiness, headache, or lightheadedness. Tamsulosin is an alpha blocker and can

cause side effects including dizziness, fatigue, nasal congestion, syncope and retrograde ejaculation. Patients who have taken alpha blockers are at risk for intraoperative floppy iris syndrome if they are going a cataracts surgery in the near future. Patients will be advised to immediately stop the medicine and seek medical care if they develop the rare but severe reactions of skin rash, swelling, confusion, irregular or fast heartbeat, eye pain, or hallucinations. As part of the standard treatment pathway for post-stent insertion, patients are also sent home with a narcotic pain medication to help with pain and discomfort. Our pathway is to prescribe all patients with 10 tabs of Norco 5/325 1-2 tabs po q6H PRN unless there are contraindications or allergies to this specific narcotic, in which case they are prescribed an alternative narcotic with Percocet 5/325 1-2 tabs po q6H PRN. Patients will be given a drug diary to document their usage of the study medications for stent discomfort, including their narcotic usage, so that this information can be tracked as well. Patients will stop drug diary at time of stent removal.

Questionnaires will be completed either in person if patient is in clinic or inpatient, or via a REDCap survey prior to stent placement, POD1, POD7 or at the time of stent removal if the removal occurs prior to day 7, and POD30. Patients with strings attach to stents will be included as there is no literature to suggest that strings cause additional stent irritation. Both medications will be stopped once the ureteral stent is removed as part of routine urological follow-up care for the primary etiology. Once the number of study participants reaches the pre-determined goal as calculated by our biostatistician, study enrollment will conclude and we will begin analyzing the data.

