# 4.2 EXCLUSION CRITERIA

- 1. Patients younger than 18 years of age
- 2. Patients with chronic or pre-existing indwelling stents
- 3. Patients currently receiving anticholinergic or alpha blocker therapy
- 4. Patients with chronic opioid or analgesic usage
- 5. Patients with chronic pain syndrome or symptomatic benign prostatic hyperplasia
- 6. Patients with an active untreated urinary tract infection
- 7. Patients who are currently pregnant or nursing
- 8. Patients with allergies or contraindication to either tamsulosin or hyoscyamine
- 9. Patients on active chemotherapy
- 10. Patients currently receiving other investigational therapy
- 11. Patients who are unable to sign consent/answer questionnaire due to compromised mental capacity or language barrier (the questionnaire is not validated in other languages)
- 12. Patients who have a stent placed emergently for an obstructing stone or septic stone without immediate stone removal,

13. Any stents placed that will stay in for longer than 2 weeks, including patients who suffered a ureteral injury (Grade 2 or above) during the procedure that will be classified as a screen fail

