# 4.3 WITHDRAWL/TERMINATION CRITERIA

Patients who do not undergo the placement of a ureteral stent following a routine urological procedure will be withdrawn from the study. If the patient was scheduled to undergo the stent placement and for any reason the plan changed or was cancelled that patient will be taken off the protocol and considered discontinued. The patient spot will be replaced and the study ID number will not be reused. This will allow the protocol to be completed once 94 patients have completed treatment based on statistical calculations from the Biostatistics department (below).

Patients will be allowed to withdraw from the study at any time. If a patient cancels permission to use their health information the research team will stop collecting any additional information about them moving forward. The research team may use and share information that was gathered before they received the patient's withdrawal. The entire study may be discontinued for any reasons without the patients consent by the investigator conducting the study.

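### Open-label randomisation at enrolment comes before stent placement and exclusion 13 are settled; patients removed in between leave an undefined modified ITT set, and removal could depend on the known arm.

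*Combined protocol and SAP*

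**What the plan says.** - **Timing of allocation.** Section 5.3: "After informed consent is obtained, the patient will be prospectively randomized to either treatment arm in an open-label fashion". The purpose is "to determine which therapy they will receive after stent placement", so study drug starts after the procedure. The schedule in 5.6 ticks Randomization under Enrollment, one column before Stent Placement.
- **Removal when no stent is placed.** Section 4.3: "Patients who do not undergo the placement of a ureteral stent following a routine urological procedure will be withdrawn from the study". If stenting was scheduled and "for any reason the plan changed or was cancelled that patient will be taken off the protocol and considered discontinued".
- **Replacement.** Section 4.3 continues: "The patient spot will be replaced and the study ID number will not be reused". It then gives the stopping rule: "This will allow the protocol to be completed once 94 patients have completed treatment".
- **Removal under exclusion 13.** Section 4.2 excludes stents that will stay in longer than 2 weeks, including after a Grade 2 or worse ureteral injury "during the procedure that will be classified as a screen fail". Exclusion 12 (emergency stent without immediate stone removal) can also turn on what is done at the procedure.
- **Analysis.** Section 5.5 declares the primary analysis intention-to-treat: "subjects will be analyzed as belonging to the arm they were randomized to, irrespective of later crossover or other modifications". It also plans a discontinuation rate by arm for patients who have to be removed. It does not say whether removed patients stay in the analysis.

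**The concern.** Allocation is open and comes first; eligibility is completed afterwards. Between the two, the clinical team decides whether to leave a stent, how to grade an injury and how long the stent should stay. The protocol has no step that keeps the arm from those making these decisions, and no arm-blind check of removals. Calling a patient a screen fail does not undo a randomisation that has already taken place.

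Two things are at stake. First, randomisation protects the comparison only if the analysed patients are those randomised, or if those left out are left out for reasons unrelated to arm. The plan secures neither. This matters more in an open-label non-inferiority trial with a patient-reported outcome, where losing patients with a poorer outlook from the hyoscyamine arm would favour a false conclusion of non-inferiority.

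Second, the analysis set is not defined. A reader of 5.5 expects all randomised patients. Sections 4.2 and 4.3 produce a smaller set with replacements, built towards a completer count. The discontinuation rate by arm may also mix never-stented patients with later drop-outs, because 4.3 labels the former discontinued.

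**Working it through.** **1. Order of events.**

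| Step | When | Source |
|---|---|---|
| Consent, then open-label randomisation | Enrollment | 5.3, 5.6 |
| Stent placed or not; plan changed | At or before the procedure | 4.3 |
| Ureteral injury grade; planned dwell over 2 weeks | At the procedure | 4.2, item 13 |
| Study drug starts | After placement | 5.3 |
| Primary outcome: change in USI, POD1 to POD7 or removal if earlier | After placement | 5.5 |

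Every removal trigger in rows 2 and 3 falls after allocation and before treatment. Replacement is explicit for row 2. For row 3 it follows only from the completer target.

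**2. The plan's own sample size.** Inputs from 5.4: one-sided alpha .025, power 80%, margin 15%, CV .25. A two-sample non-inferiority t-test with true difference 0, margin .15 and SD .25 (both as fractions of the mean) needs 45 per arm; the plan states about 47. At 47 per arm, power on this scale is 82.1%. Ratio and log-scale variants run from 38 to 52, and the plan does not name its scale, so 47 is not in dispute. Total: 2 × 47 = 94.

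**3. What the gap between 94 and 100 covers.** 94 / (1 − .06) = 100, so the stated total allows for 6% loss. Reaching 94 completers would take, at assumed loss rates:
- 10%: 94 / .90 = 104.4, so 105 randomised
- 15%: 94 / .85 = 110.6, so 111
- 20%: 94 / .80 = 117.5, so 118

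The documents give no expected rate.

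**4. Can the bias be sized?** Not for the planned primary test. That test uses the change from POD1 to POD7 with a margin of 15% of the change, and 5.5 says the POD1 data are too sparse for a good estimate of the change. A severity effect common to both days would cancel in the change.

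On the sample-size scale only, as an illustration with assumed inputs (higher USI is worse, 47 per arm kept by replacement, true difference at the margin):
- SE of the difference = .25 × √(2/47) = .0516.
- Assume the 10% with the worst expected symptoms are removed from one arm only, and that expectation correlates .5 with USI. The shift in that arm's mean is φ(1.2816)/.90 × .5 × .25 = .1755/.90 × .125 = .0244, or .0244/.15 = 16% of the margin.
- In SE units: .0244/.0516 = .473.

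| Pattern of removal | One-sided type I error |
|---|---|
| Independent of arm | Φ(−1.96) = 2.5% |
| Worst patients lost from hyoscyamine | Φ(−1.96 + .473) = 6.8% |
| Worst patients lost from tamsulosin | Φ(−1.96 − .473) = 0.7% |

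The 10% and the correlation are not in the documents. The table shows only that the error can move either way and need not move at all.

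**The case against.** The strongest reply is that the removal triggers are clinical, and that the protocol describes both drugs as routine in this practice. It gives no reason why allocation to one of them would change whether a stent is left, how an injury is graded or how long the stent stays. Patients who never get a stent take no study drug and have no stent symptoms to score, so leaving them out for pre-treatment reasons gives a familiar modified ITT set. The rate of discontinuation by arm could also reveal unequal removal.

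Much of this stands, and it rules out several stronger readings:
- **That the arms will be biased.** A reader might infer this from the sequence. The documents show an open route, not that anyone takes it.
- **That everyone knows the arm before surgery.** Open-label does not say that the surgeon is told beforehand. Equally, nothing withholds it.
- **That all removed patients are replaced.** Section 4.3 says so only for patients with no stent or a changed plan.
- **That the ITT claim fails altogether.** For stented patients who stay in the study, the rule in 5.5 on crossover is sound. The gap concerns those removed before treatment.
- **That the pre-stent USSQ is contaminated by knowledge of the arm.** Section 5.1 describes consent followed by the first questionnaire, although the order relative to randomisation is not fixed. That score does not enter the primary analysis.

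What does not stand is the comfort taken from the planned rate. A rate by arm, not split by reason or timing, can show unequal numbers but not whether patients with a different outlook were lost. And a modified ITT set is acceptable only if it is defined in advance and its exclusions cannot depend on arm; here neither is secured.

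**Conclusion.** The concern holds as a design weakness. Patients are randomised openly before eligibility is complete. Some are then removed, and some of those are explicitly replaced. The analysed set is therefore an undefined modified ITT set and not everyone randomised. This follows directly from 4.2, 4.3, 5.3, 5.5 and 5.6 and rests on no assumption.

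The effect on the result is possible but not shown, and its size in the primary test cannot be derived from the documents. If removal is independent of arm, type I error stays at 2.5% and the damage is to the label and the reporting. The 6.8% and 0.7% above describe one assumed removal pattern on the single-time-point scale and should not be quoted as the error rate of the planned test. The change is worth making because the weakness is avoidable: study drug starts only after placement, so nothing stated requires earlier allocation.

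**What to change.** 1. Keep consent and the pre-stent USSQ before the procedure. Run the REDCap randomisation only after the stent is placed and exclusions 12 and 13 have been checked.
2. Move the Randomization tick in 5.6 from Enrollment to Stent Placement, and align 4.2, 4.3 and 5.3. Patients who fail before that point are then true screen failures.
3. State in 5.5 that everyone randomised is analysed in the assigned arm, including those whose stent dwell is extended afterwards.
4. Replace the completer target in 4.3 by a number randomised, for example the stated total of 100, with no replacement after randomisation. Without this step, later losses would still be replaced.

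If randomisation cannot be moved, the fallback is to define the modified ITT set in advance and report removals by arm, reason and timing. That makes the problem visible but does not remove it.

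**Cost.** A short amendment, and staff must trigger randomisation at the end of the procedure. The 47 per arm requirement is unchanged, and there are no extra visits or data. With 100 randomised and no replacement, only losses after placement reduce power. On the simple difference scale, 6% loss leaves 47 per arm (82.1%), 10% leaves 45 (80.4%), 15% leaves 42 (77.6%) and 20% leaves 40 (75.5%). If the sponsor expects more than about 10% loss after placement, the number randomised should be raised in the same amendment.
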